Acute intermittent hypoxia (AIH) induces spinal plasticity, strengthening connections to motor neurons.⁶⁻¹⁰ Considerable progress has been made towards an understanding of cellular mechanisms giving rise to AIH-induced respiratory plasticity.⁸ Repetitive exposure to AIH enhances the expression of plasticity-promoting proteins in respiratory motor nuclei¹⁰⁻¹² and elicits profound recovery of breathing capacity in spinally injured rats.¹³ Key steps in AIH-induced plasticity include episodic release of serotonin near respiratory motor neurons, initiating new synthesis of brain derived neurotrophic factor (BDNF) and subsequently activating its high affinity receptor, TrkB⁶. “Downstream” events include the activation of extracellular signal-regulated kinases (ERK); mitogen-activated protein (MAP) kinases and postulated insertion of glutamate receptors at the synapse between respiratory pre-motor and motor neurons. Excitingly, these changes extend beyond the respiratory system. Colleagues also observed that AIH enhances expression of these same proteins in *non-respiratory* motor neurons.⁹

Although dAIH may be a viable method to enhance walking after iSCI, the mechanisms underlying dAIH-induced motor recovery may be constrained by competing neural mechanisms of motor facilitation. While dAIH induces facilitation predominantly via serotonin-dependent mechanisms¹⁴, even mild hypoxia causes ATP release from glia and other sources in the nervous system, leading to an accumulation of extracellular adenosine. Subsequent activation of A_{2A} receptors elicits a distinct form of motor facilitation¹⁵ that is known to compete with the serotonin-dependent pathway via cross-talk inhibition^{16, 17}. Consequently, systemic administration of a selective A_{2A} receptor antagonist, MSX-3, reduced cross-talk inhibition and increased AIH-induced long-term motor facilitation in the phrenic and hypoglossal nerves by nearly 50% and 20%, respectively, in rats¹⁷. The impact of adenosine A_{2A} receptor antagonists on AIH-induced motor recovery have not yet been studied in persons with incomplete SCI (iSCI).

Our working hypothesis is that reducing crosstalk inhibition during dAIH with a well-tolerated A_{2A} antagonist (caffeine) will enhance AIH-induced improvement of walking function in persons with chronic iSCI.

8. Objectives

The main objective of this clinical trial is to evaluate the effects of a common, safe adenosine A_{2A} antagonist, caffeine, on recovery of walking following dAIH in persons with chronic iSCI. While highly specific A_{2A} receptor antagonists, such as MXS-3 and ZM2412385, block cross-talk in rats,¹⁷ their safety in SCI is not known. On the other hand, caffeine offers the ideal blend of known

safety, metabolism, and efficacious A_{2A} receptor antagonism.¹⁸ Even at low plasma concentrations (1-10µM) after one cup of coffee, caffeine antagonizes A_{2A} receptors,¹⁸ and the efficacy of moderate caffeine in blocking neural A_{2A} receptors is illustrated by the neuroprotective effects of regular caffeine consumption in dopaminergic transmission in Parkinson's Disease.¹⁹ Although caffeine has many neurobiological actions, caffeine's actions at physiologically relevant doses (1-100 µM), including the proposed dose of up to 6 mg/kg body weight, are mediated by adenosine receptor antagonism versus phosphodiesterase inhibition, release of intracellular calcium stores, or other site.²⁰ Our study will quantify the daily (5 consecutive days) effects of caffeine (e.g., 4 mg/kg) as an adjunctive therapy to dAIH for restoring walking function in persons with chronic iSCI. This dose has known safety in iSCI and substantial antagonism to A_{2A} receptors.^{18, 21, 22}

III. Methods: Participants, interventions, and outcomes

9. Trial Design

We will conduct a placebo-controlled, cross-over, block-randomized intervention study to assess the efficacy of daily caffeine prior to AIH on improving walking function in persons with chronic, motor-incomplete SCI.

10. Randomization

Assignment of interventions for study participants will be done using allocation sequence generation, concealment, and double-blinded implementation.

- Allocation sequence generation – This study will consist of three blocks: caffeine+AIH, caffeine+SHAM, and placebo+AIH. We will generate the blocked randomization for the study participants using a random number list randomizer (Random.org).²³ Participants will randomly receive each intervention block with a minimum of 2-week wash-out between blocks. We will analyze *post hoc* differences in age, impairment score, assistive device used, baseline lower extremity motor scores, and male-female ratio using independent t-tests.
- Concealment mechanism – We will conceal the intervention allocation from the evaluators performing the assessments, treatment administrators, and the study participant.
- Implementation – The PI and biostatistician will generate the allocation sequences for the cross-over study. The trial coordinator will enroll participants and study staff who are not training or assessing the participants will assign the block randomized interventions.

11. Sample size

Twenty individuals with chronic (> 6 months post injury), motor-incomplete SCI (i.e., American Spinal Injury Association Impairment Scale (AIS) C or D) will be recruited for the study. Prior to the start of this clinical trial, we estimated the number of participants needed to achieve study objectives. In particular, our sample size computation focused on treatments: caffeine+dAIH versus placebo+dAIH alone. Our preliminary study on the effects of caffeine prior to single AIH sequence (vs placebo+SHAM) on 10MWT showed a decrease of 2.4s±1.2s. Under the hypothesis of an additive effect of caffeine+dAIH (vs. placebo+dAIH), we anticipate the difference in walking speed (10MWT time) change between treatments would be approximately 0.06m/s. With N=20 cross-over participants (includes 17% attrition rate), a repeated measures ANOVA comparing 4 treatments across 4 time points, using pooled SD of 1.3s across days, will be sensitive to detect a difference at power of $1 - \beta = 0.80$ ($f=0.7$, $F_{3,12}=3.5$; $p=0.4$, $\alpha=.05$).

12. Framework

This placebo-controlled study will examine the combined effects of caffeine and AIH results in greater walking performance than either intervention alone. However, this trial will not evaluate the potential superiority or equivalence of caffeine+AIH to standard of care treatments for persons with chronic iSCI.

13. Statistical interim analyses and stopping guidance

We do not plan to conduct an interim analysis. However, we will impose criteria for discontinuing or modifying allocated interventions. The interventions will be stopped, and immediate care provided if any significant adverse effects, such as rapid heart rate, dizziness, nausea, or a significant change in blood pressure, are detected or self-reported by the study participant. Participants with diabetes, cirrhosis, a history of autonomic dysreflexia, caffeine allergies or sensitivities, or females who are pregnant will be excluded from this portion of the study. Due to the diuretic effects of caffeine, subjects will be asked to empty their bladders prior to consumption. During and between interventions, blood pressure and heart rate will be monitored. Any adverse effects will be reported and assessed. Our study team will be prepared to discontinue treatment and offer immediate care if any significant adverse effects, such as rapid heart rate, systemic hypertensive event, dizziness, or nausea are detected or self-reported by the subject. We will define a systemic hypertensive event as a systolic pressure exceeding 140 mmHg and/or diastolic pressure exceeding 90 mmHg.^{24, 25} We will stop this trial if serious adverse events are directly attributed to the interventions under study.

14. Timing of analysis

All outcomes will be analyzed collectively. We will maintain concealment of the intervention allocation until the completion of data collection.

15. Timing of outcome assessments

Timing of outcome assessments will occur during specified visits. The timepoints of these assessments along with the timepoints for enrollment and interventions are detailed in the timing schedule (Table 1).

Table 1. Timing Schedule for enrollment, interventions, and assessments

Timepoints (days)	Enrollment		Baseline		Intervention			Follow-ups/Washout	
	-5	0	1	2	3	4	5	8	14
Screening and Allocation Timing									
Eligibility screen	x								
Informed consent	x								
Medical clearance	x								
Allocation		x							
Drug script		x							
Intervention Timing									
Placebo+AIH			x	x	x	x	x		
Caffeine+AIH			x	x	x	x	x		
Caffeine+SHAM			x	x	x	x	x		
Assessment Timing									
Primary outcome									
• Walking speed (10MWT, s)		x				x	x	x	
Other outcomes									
• Voluntary leg strength	x				x	x	x	x	
• Spasticity	x				x	x	x	x	
• Spasm frequency	x				x	x	x	x	
• Walking function	x				x	x	x	x	
• Walking distance (6MWT, m)	x				x	x	x	x	
• Walking Balance (TUG, s)	x				x	x	x	x	
• Blinding Questionnaire		x	x	x	x	x			
• Weight (kg)	x						x	x	
Safety Outcomes									
• Pain (0-10)	x	x	x	x	x	x	x	x	
• Blood pressure (mmHg)	x	x	x	x	x	x	x	x	
• Heart rate (BPM)	x	x	x	x	x	x	x	x	
• Oxygen saturation (%)	x	x	x	x	x	x	x	x	
• Memory (0-30)	x	x	x	x	x	x	x	x	
Biomarkers									
• CYP1A2 Polymorphism	x								
• Caffeine serum level (mg/L)		x				x			
• Inflammation (CRP)		x			x		x		

IV. Statistical Principles

We plan to use a parametric linear mixed model since this method is sensitive to within subject changes and robust against variability, small sample sizes, and missing/unbalanced data sets as compared to other statistical models.²⁶ If the results do not meet these model assumptions, we will apply alternative non-parametric tests.

16. Level of significance

All applicable statistical tests will be 2-sided and will be performed using a 5% significance level.

17. Adjustment for multiplicity

we do not plan to adjust for multiplicity.

18. Confidence intervals

Statistical comparisons will include 95% (2-sided) confidence intervals (CIs).

19. Adherence and protocol deviations

We will record a deviation (if the even does not significantly affect a participant's rights, safety, or well-being, or trial outcomes), or a violation (if the deviation may potentially significantly impact the completeness, accuracy, and/or reliability of the trial data or that may significantly affect a patient's rights, safety, or well-being). All protocol deviations/violations will be logged, but no formal statistical testing will be performed.

Adverse events will be reported on an IRB-approved electronic Case Report Form (eCRF). Details will include the type of event, date of onset, duration, intensity, causality relationship to the study drug(s), and outcome. If an adverse event should occur, every attempt will be made to obtain as much information as possible about event evaluation and outcome. If a serious adverse event occurs, the treatment will be interrupted or discontinued at the physician investigator's discretion. All protocol deviations will be reported to the PI ([name]) and the IRB.

[name] will fulfill the responsibilities identified in the study's delegation log. These responsibilities include collecting and tracking data forms and instituting quality control measures for data entry verification and study compliance. She will request further documentation such as physician and/or procedure notes in the event of observed or reported adverse events or deviations. They also will be responsible for auditing the database and confirming the overall integrity of the data. The PI ([name]) will ensure that all information pertaining to significant new developments and unanticipated adverse events are provided to the appropriate regulatory authorities, the Investigators, and to the IRB. Quality control measures for this study will be conducted at regular intervals ensure the highest standard of clinical research conduct. These inspections are conducted in order to verify adherence to the protocol and the completeness and accuracy of the data.

20. Analysis populations

In this cross-over trial, participants will receive the primary intervention (caffeine+AIH) as well as the control conditions (placebo+AIH, caffeine+SHAM). We will perform safety-related assessments on each study participant. We anticipate all participants will participate in the 3 interventions as prescribed, will attend all test visits, and will not have any serious protocol violations.

V. Trial Population

21. Screening data

There will be no statistical testing completed for clinical characteristics. We will summarize the sex, duration of SCI, level and severity of SCI, age, weight, as well as biomarker measures (see Table below). The categorical data will be presented using counts and percentages. The continuous variables (e.g., outcome measures) will be presented using the mean, median, standard deviation (SD), minimum, maximum, and number of participants with an observation (n).

22. Eligibility

Potential subjects will be informed about the objectives of the study and must meet all inclusion and exclusion criteria (see Appendix 1 for sample Informed Consent Form). They will be required to read and sign approved consent and HIPAA forms prior to participation to allow access to medical information from their physicians.

Inclusion criteria: Participation requirements for SCI participants include: 1) 18 to 75 years old; 2) medically stable with medical clearance from physician to participate; 3) SCI at or below C₂ and at or above L₅ with at least some lower extremity motor function preserved below the neurologic level; 4) non-progressive etiology of spinal injury; 4) AIS A-D at initial screen; 5) at least 6 months post-injury (chronic). We plan to choose subjects greater than 6 months post-injury to ensure minimal confounding effects of spontaneous neurological recovery during the experiments. This will mean that changes in sensorimotor performance are more likely due to the interventions associated with the research study.

Exclusion criteria: Individuals will be excluded due to: 1) severe concurrent illness or pain, including unhealed decubiti, severe neuropathic or chronic pain syndrome, infection (e.g. bladder), hypertension, cardiovascular disease, pulmonary disease, severe osteoporosis (history of fractures), active heterotopic ossification in the lower extremities, or history of peripheral nerve injury in the legs; 2) < 24 on Mini-Mental Exam ²⁷; 3) severe autonomic dysreflexia; 4) history of cardiovascular/pulmonary complications; 5) pregnancy because of unknown effects of AIH on a fetus, although women of childbearing potential will not otherwise be excluded; 6) undergoing concurrent physical therapy; 7) history of diabetes. Caffeine can potentially alter sugar metabolism and, thus, persons diagnosed with diabetes will be excluded from participating in the caffeine portion of this study; 8) history of cirrhosis. Cirrhosis is known to increase the elimination time of caffeine and, thus, persons diagnosed with cirrhosis will be excluded from participating in the caffeine portion of this study; and 9) history of caffeine allergies or intolerances. Participants with a history of caffeine allergies or intolerances will be excluded from participating in the caffeine study.

Inclusion of women and minorities: We will recruit persons with SCI to include women and minorities. To protect against possible unknown side effects of dAIH, women who are pregnant may not take part in this study as the effects of dAIH on the developing fetus have not been studied. If a woman is of childbearing ability, birth control will be recommended for use throughout the study.

Our study coordinator, study physicians, physical therapists, PI ([name]), and research collaborators recruited subjects using a variety of strategies shown effective in the past. First, the team identified potential subjects using Institutional Review Board (IRB) approved resources to inform persons with SCI that are currently admitted to inpatient rehabilitation/outpatient units of Spaulding Rehabilitation Hospital, Boston University Medical Center, Massachusetts General

Hospital, Gaylord hospital, Albany Medical Center, and Maine Medical Center. Subjects also will be recruited by word of mouth and flyers at these facilities. Eligible subjects screened at INSPIRE Laboratory, Spaulding Rehabilitation Hospital Cambridge, MA. At the screening visit, subjects informed of this project, their potential involvement, the possible benefits, and risks, and their right to terminate participation at any time without penalty. Qualifying subjects in agreement with the study details asked to sign the informed consent and HIPAA form approved by Partners IRB. All potential subjects entered the study according to the inclusion/exclusion criteria above and following medical clearance. Experiments will be conducted at the Spaulding Rehabilitation Hospitals.

23. Recruitment

Our study coordinator ([name]), study physicians ([name], [name]), physical therapists, PI ([name]), and research collaborators will recruit subjects using a variety of strategies shown effective in the past. First, the team will identify potential subjects using Institutional Review Board approved resources to inform persons with SCI that are currently admitted to inpatient and outpatient settings at Spaulding Rehabilitation Hospital, Boston University Medical Center, Massachusetts General Hospital, Gaylord Hospital, Albany Medical Center, and Maine Medical Center. Subjects will be recruited by word of mouth and flyers at these facilities. This project also will have access to clinical resources at Spaulding Rehabilitation Network.

Prospective participants will be contacted initially by phone or in-person and informed of the methods, inclusion/exclusion criteria, and purpose of the study. We also will provide a description of this study on ClinicalTrials.gov (NCT02323698), as required by U.S. law. In all cases, recruitment will not be coercive, will not involve undue inducements, and will accurately reflect the study.

Potential subjects will be identified by the following sources:

- Attending physicians or therapists may refer their subjects to the study. We will provide physicians, therapists, and clinics with study information sheets, letters, and flyers. Prospective subjects will be encouraged to contact the study co-investigators.
- Flyers posted in public areas across the Boston-land region, in the outpatient specialist clinics, or other private locations with given permission.
- Internet, e-mail, digital signage, and newspaper advertisements.
- Advertisings posted in Boston public transportation (The T).
- Patients who have received care within the Mass General Brigham Healthcare system will be recruited Patient Gateway. We will use the Research Patient Data Registry (RPDR) to identify potential participants using strict search criteria which will include spinal cord injury diagnosis, age (18 to 75), and date of injury; we will exclude individuals who have “opted out” of receiving research announcements.
- Possible participants may also be identified through their medical records and their physicians might be asked to inform the subjects about the study.
- Presentations at local, state hospitals, and rehabilitation facilities that include public and VA medical centers in the U.S. Northeast (such as to rehabilitation staff and support groups at Spaulding and Partners Network, Boston University Medical Center, Gaylord Hospital, Albany Medical Center, and Maine Medical Center).

- Attending public forums, conferences, or events at which the co-investigator will distribute IRB approved recruitment materials.
- Social Media: Google Ads, Facebook, and Twitter – all advertisements will be submitted to (the way they appear on any social media site) and approved by the IRB prior to posting.
- Partners clinicaltrials.partners.org site.
- We will contact patients who have consented to be added to the Spaulding Rehabilitation Hospital's Spinal Cord Injury Model Systems (SCIMS) Database who have identified that they wished to be contacted for additional research studies. Research staff recruiting from the SCIMS database are also added as study staff on the SCIMS protocol.

Eligible participants will be screened at the designated site facilities (i.e., INSPIRE Laboratory, Spaulding Rehabilitation Hospital at Boston and at Cambridge sites). At the screening visit, subjects will be informed of this project, their potential involvement, the possible benefits and risks, and their right to terminate participation at any time without penalty. Qualifying subjects in agreement with the study details will be asked to sign the informed consent and HIPAA form approved by Spaulding Rehabilitation Hospital's IRB. All potential subjects will enter the study according to the inclusion/exclusion criteria above and following medical clearance. Experiments will be conducted at the Spaulding Hospital in Cambridge.

Prospective subjects will be contacted by telephone, mail or email and briefly informed of the methods, inclusion criteria, and purpose of the study. We also will provide a description of this study on <http://www.ClinicalTrials.gov>, as required by U.S. law. In all cases, recruitment will not be coercive, will not involve undue inducements, and will accurately reflect the study.

We will recruit individuals who reflect the population of persons with SCI in the Northeast region of the United States, which is 19% women, 81% men, 67% Caucasian, 24% African American, 8% Hispanic, 2% Asian, and 1% Native American. We do not yet know of any differences in responsiveness to AIH or caffeine according to the gender or race of persons with SCI.

Children will not be included in this study. The proposed research is aimed at understanding the plasticity-inducing mechanisms of caffeine and repetitive acute intermittent hypoxia exposure in adults with chronic, incomplete spinal cord injury. A separate study would be required to address the confounding effects of childhood growth and development after spinal injury on the proposed intervention study – a topic best suited for future research once the underlying mechanisms of the intervention are better characterized.

24. Withdrawal/follow-up

We will compute the completeness of follow-up as a ratio depicting the proportion of participants with a complete follow-up 10MWT time after randomization relative to the number of participants enrolled. There will be no statistical testing completed for assessing the adherence to allocated treatments. Reasons for lost data will be documented and detailed in the study's CONSORT flow diagram.

25. Baseline patient characteristics

VI. Analysis

26. Outcome definitions

The primary outcome measure is change in walking speed (10MWT time, s) relative to baseline (BL). For all analyses, we will use the average of two 10MWT times at BL, D₅, F₁, and F₂. Change

in walking speed will correspond to the difference between post-intervention 10MWT and BL times. Please review Table 1 for timing of outcome assessments.

All the summaries in this section will be equivalent to the main and the final results reports. There will be statistical testing completed for baseline testing of the primary outcome measure (10MWT). Since we plan to use a cross-over study design, we will compare the 10MWT baseline measurements between the interventions to evaluate the effects of the washout period.

Assessment and collection plans: Physical evaluations will be completed by the study's licensed physical therapists or occupational therapists and/or trained research study staff. Functional ability of subjects will be evaluated using standard clinical assessments with high inter-rater reliability: American Spinal Injury Association Impairment Scale (AIS) lower extremity motor scores (LEMS) to quantify strength,²⁸ and Spinal Cord Assessment Tool for Spastic Reflexes (SCATS), and the Penn Spasm Frequency Scale (PSFS) which is a self-report assessment of the frequency and severity of muscle spasms²⁹ and modified Ashworth Scale to quantify spasticity.³⁰ We also will record pain severity using the well-established Wong-Baker FACES scale, which shows high test-retest reliability and interpretability as well as good content and construct validity.^{31,32} Clinical ratings of walking ability, including Walking Index for Spinal Cord Injury (WISCI) II³³ and/or SCI Functional Ambulation Index (SCI-FAI),³⁴ will be assessed based on video recordings of the 10MWT.

We will quantify secondary measures of walking function using the timed up-and-go test (TUG, walking initiation and balance), six-minute walk test (6MWT, walking endurance). These tests capture functional ambulation as well as the ability to initiate walking, exhibit high reliability and construct validity.³⁵ Participants will perform 2 trials each of the TUG at their fastest but comfortable and safe speed with a minimum of 1-minute rest between trials. Average speed across the 2 TUG trials will be used for analyses. Subjects will perform the 6MWT once at their fastest, comfortable walking speed sustainable for 6 minutes. Distances will be recorded at 2 and 6 minutes. Participants will use their least restrictive assistive device during these walking assessments.

27. Analysis methods

We plan to analyze within-participant pre-post changes in walking speed (10MWT) for each intervention. We plan to use a parametric linear mixed model for comparing our outcome measure since this method is sensitive to within subject changes and robust against variability, small sample sizes, and missing/unbalanced data sets as compared to other statistical models.²⁶ If the results do not meet these model assumptions, we will apply alternative non-parametric tests.

All data will be managed using REDCap³⁶, MS 365 Excel 16.54 (Microsoft, USA), and MATLAB R2020a (Mathworks Inc, USA) and will be analyzed using SPSS[®] Statistics 26 (64-bit edition, IBM, USA). Descriptive statistics, including means, standard deviations and 95% confidence intervals of the within-participant pre-post change for each intervention will be calculated for all measures. The baseline characteristics of the participants will be compared using parametric and non-parametric inferencing.

Hypothesis testing: To evaluate our main hypothesis that caffeine prior to AIH enhances walking recovery, we will perform a linear mixed model with fixed effects at a significance at the p=0.05 level.³⁷ Intervention (caffeine+dAIH, caffeine+SHAM, placebo+dAIH) and time (day) will be the fixed main effects, with subject as random effect and walking speed (10MWT) as repeat measures. Differences from BL will be compared between and within interventions at D₅, F₁, and F₂.

Bonferroni corrections will be made for multiple comparisons.

Alternative statistical methods: If distributions are not normal, we will perform comparable nonparametric tests. If baseline measures are significantly different between sessions (interventions), an analysis of co-variance (ANCOVA) will be used to analyze the data.

Blinding integrity analysis: we plan to rigorously quantify blinding integrity here. We will ask participants and raters to guess the intervention received at the end of each intervention and indicate guess confidence using a Likert scale.^{38,39} We will use a contingency table and Fischer's Exact Test to determine if the probability of correct guessing is different from chance. Using multivariate logistic regressions, we also will assess factors that may influence guessing (i.e., adverse events, perceived effects, and sensorimotor changes). In the event of a medical emergency, we will unblind the PI, study participants, and care provider. We also will notify IRB of treatment allocation during adverse event reporting as necessary.

CYP1A2 analysis: we will perform subgroup analysis on our study cohort to determine the extent to which differences in caffeine metabolism due to CYP1A2 polymorphisms may affect responsiveness to the combinatorial treatment of caffeine+AIH.

28. Missing data

Rigorous efforts will be made to ensure complete outcome data. However, we anticipate that participants in this study cohort may be unable to complete the study requirements. Missing data will be reported and documented as we did in our previous clinical trial.⁴⁰ We will document reasons for missing data and our approach to handle missing data during statistical analysis. We will account for potential outliers in our results using a conservative outlier labeling technique set forth by Hoaglin and Tukey.⁴¹

29. Additional analyses

We do not anticipate any additional statistical analyses methods.

30. Harms

Checklists and note pages are used to log any deviations or omissions from the protocols. Any clinical/health related issues would be immediately presented to the subject to determine appropriate notification (i.e., current physician or appropriate specialist). Based on the seriousness of the situation Drs. [name] or [name] may be contacted to provide clinical guidance on the appropriate course of action as per our Laboratory Medical Emergency Safety Plan.

31. Statistical software

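### The 80% power is stated at an uncorrected 5% level, while two sections put the sized comparison under Bonferroni and SAP 17 says there is no adjustment

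*Combined protocol and SAP*

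**What the plan says.** The sample size text is the same in Protocol 14 and SAP 11. It says that "our sample size computation focused on treatments: caffeine+dAIH versus placebo+dAIH alone", and that with 20 participants, dropout included, the design "will be sensitive to detect a difference at power of" 0.80. The printed inputs are f = 0.7, F(3,12) = 3.5, p = 0.4 and α = .05. The test named is "a repeated measures ANOVA comparing 4 treatments across 4 time points, using pooled SD of 1.3s across days".

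The hypothesis-testing paragraphs of Protocol 20 and SAP 27 fit a linear mixed model at the 5% level with three interventions. Both then say "Differences from BL will be compared between and within interventions at D₅, F₁, and F₂" and "Bonferroni corrections will be made for multiple comparisons". Neither gives the number of comparisons or names a primary visit, and neither takes any contrast out of the correction.

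SAP 16 sets a two-sided 5% level for all applicable tests, SAP 17 says no multiplicity adjustment is planned, and SAP 18 calls for 95% confidence intervals.

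**The concern.** The sample size is justified by one comparison, caffeine+dAIH against placebo+dAIH, at the full 5%. On the hypothesis-testing text of both documents, that comparison is one of several that share the 5%. A contrast with 80% power at .05 has less at .05/k, and nothing in the sample size section allows for this.

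The stated 80% is the figure against which a null result on the main question will be read. If the test is run at a Bonferroni level, a true effect of the assumed size is missed more often than the stated one time in five, and a null finding would be given too much weight. Because SAP 17 contradicts SAP 27 and Protocol 20, a reader cannot tell which level applies.

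**Working it through.** **1. The level used in the plan's calculation.** The upper 5% point of F on 3 and 12 df is 3.490, and P(F > 3.5) = 0.0496. The printed F is therefore the critical value at an uncorrected .05.

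**2. The plan's own 0.80.** I read the printed p = 0.4 as the correlation between repeated measures, which is an assumption. Two layouts give 3 and 12 df.
- Between-factor, N = 16, 4 groups, 4 measures: λ = f²·N·m / (1 + (m − 1)ρ) = 0.49 × 16 × 4 / 2.2 = 14.25, power 0.773.
- Within-factor, N = 5, 4 measures: λ = f²·N·m / (1 − ρ) = 0.49 × 5 × 4 / 0.6 = 16.33, power 0.831.

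Neither gives 0.80 at the printed inputs, but rounding could explain the gap: f = 0.72 in the first layout gives 0.798, and 16 / (1 − 0.17) = 19.3 rounds up to 20. In every case the figure belongs to an omnibus four-treatment F test. For the next steps I grant 80% to the two-treatment contrast for the sake of argument.

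**3. Inputs for the contrast.** Two-sided .05 comes from SAP 16 and SAP 11. The plan says "With N=20 cross-over participants (includes 17% attrition rate"), so completers are about 20 × 0.83 = 16.6. A paired contrast then has n − 1 = 15 to 19 df. Error pooled over three treatments would have about 2(n − 1) = 30 to 38 df.

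**4. Formulas.**
- Normal approximation: power(k) = Φ(z₀.₉₇₅ + z₀.₈₀ − z₁₋₀.₀₂₅/ₖ) = Φ(1.960 + 0.842 − z₁₋₀.₀₂₅/ₖ). For k = 3, the last term is 2.394, so Φ(0.408) = 0.658.
- Noncentral t: solve for the standardized effect that gives 0.80 at .05 (0.660 for n = 20, 0.724 for n = 17, 0.749 for n = 16), then recompute at .05/k.

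**5. Results.** The documents do not define the family, so each k is an assumption.

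| k | Possible family | t, 15–19 df | t, 30–38 df | Normal |
|---|---|---|---|---|
| 1 | no adjustment (SAP 17) | 80% | 80% | 80% |
| 2 | the two contrasts predicted in Protocol 20, one visit | 69.2–69.7% | 70.3–70.5% | 71.2% |
| 3 | all pairwise contrasts, one visit | 62.4–63.1% | 64.2–64.5% | 65.8% |
| 6 | the two predicted contrasts, three visits | 50.6–51.8% | 53.6–54.2% | 56.5% |
| 9 | all pairwise contrasts, three visits | 43.9–45.4% | 47.5–48.3% | 51.1% |

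Counting the nine within-intervention comparisons (three interventions at three visits) in the same family would make k = 18 and lower the power further. I leave that case out of the range, because nothing says the within and between comparisons share one correction.

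**The case against.** Three points can be made for the plan.

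First, SAP 17 rules out adjustment, and SAP 16 and 18 keep the 5% level and 95% intervals. On those sections the contrast is tested at .05 and the loss is zero. This stands, and it makes the point conditional. It does not remove it: Bonferroni appears in both documents, in the paragraphs that specify the hypothesis test. If the conflict is settled in favour of Bonferroni, the power statement still needs changing.

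Second, the printed calculation is an omnibus test, and the mixed model is also assessed at .05, so like matches like. This is right about the printed 0.80. But the plan says the computation focused on two named treatments. An omnibus intervention effect among three arms does not show that caffeine+dAIH beats placebo+dAIH. That question is answered by the pairwise comparison, which is where the correction applies.

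Third, the family may be small. This also stands. A reader might infer a ceiling of 63% power, or that at least 37% of true effects would be missed, because three interventions give three pairwise contrasts. The documents do not support such a bound. Protocol 20 predicts only two contrasts, which at one visit gives 69–71%; even with three comparisons the result reaches 64–66% with more error df or the normal approximation.

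**Conclusion.** The power statement and the multiplicity rules do not fit together and should be corrected. If Bonferroni governs, an assumed 80% at two-sided .05 becomes about 69–71% for 2 comparisons, 62–66% for 3, 51–57% for 6 and 44–51% for 9. The chance of missing the assumed effect rises from 20% to about 29–31%, 34–38%, 43–49% and 49–56% respectively. If SAP 17 governs, there is no loss from this source.

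The ranges rest on assumed family sizes and on granting 80% to a within-person contrast. They should not be read as the trial's actual power. The printed 0.80 is for a four-treatment omnibus test in a three-intervention trial. The expected effect is given in speed ("we anticipate the difference in walking speed (10MWT time) change between treatments would be approximately 0.06m/s") and the SD in seconds, with no baseline speed to convert one to the other. The power of the named contrast therefore cannot be worked out from the documents.

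**What to change.** 1. Reconcile SAP 17 with SAP 27 and Protocol 20, so that one multiplicity rule applies.
2. If Bonferroni is kept, list the comparisons in the family: which contrasts, which visits, and whether the within-intervention comparisons count.
3. In SAP 11 and Protocol 14, restate the power for caffeine+dAIH versus placebo+dAIH at the level at which that contrast will be tested.

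As an option, the sponsor could name that contrast at one stated visit as primary at two-sided .05 and apply Bonferroni to the rest. This is a trade-off and not a required correction. The other visits and the comparison with caffeine+SHAM would become supportive, although SAP 12 aims to beat either intervention alone and Protocol 20 predicts both contrasts.

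The cost is wording in both documents and one recalculated figure. No more participants are needed. The downside is a less favourable stated power or, under the option, a narrower primary claim.
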